14.2.2. Severity of adverse events

The investigator should assess the severity of the AE (i.e. intensity) using the following scale:

Grade 1 (Mild): Asymptomatic or with mild symptoms that do not require corrective treatment.

Grade 2 (Moderate): Requiring minimal local or non-invasive corrective treatment.

Grade 3 (Severe): Medically significant but not immediately life-threatening; indication for

hospitalization or prolongation of hospitalization; disabling.

Grade 4: Life-threatening, requiring emergency treatment.

Grade 5: AE-related death.

14.2.3. Accountability for Adverse Events

In accordance with Regulation (EU) 2017/745 on medical devices, the relationship between the use of the device under investigation, including the comparator device or investigation procedures, and the occurrence of each adverse event must be assessed and classified according to 4 levels of imputability (1/ Unrelated, 2/ Possible, 3/ Probable, 4/ Causal relationship).

The sponsor and investigators will use the following definitions to assess the relationship between each adverse event (non-serious or serious) and the device under investigation or comparator or the investigational procedures:

- 1) **Unrelated:** the imputability of the device or protocol may be excluded when:
 - The event is not known to be a side effect of the product category to which the device under investigation belongs or to a similar device and/or protocol,
 - The time taken for the event to emerge appears to be incompatible with the use of the medical device under investigation or with the procedures involved.
 - The event does not follow a response pattern known to the medical device (if the response pattern is already known) and is biologically implausible.
 - Stopping the use of the medical device or reducing its level of use (when clinically possible) and then resuming its use or increasing its use had no impact on the event.
 - The event affects a part of the body or an organ whose impact by the device or by the protocol is not expected.
 - The event may be attributed to another cause (e.g. an underlying or concomitant disease/health condition, the effect of another device, another drug, another treatment or another risk factor).
 - The damage suffered by the subject is clearly not due to an error in use.
 - In order to establish the absence of a causal link, it is not necessary for all of the above criteria to be met; it depends on the type of device/protocol and the event.
- 2) **Possible:** the relationship with the use of the device is weak but cannot be totally ruled out. Alternative causes are also possible (e.g. an underlying or concomitant disease/condition and/or an effect of another device, drug or treatment). Cases in which imputability cannot be assessed or no information has been obtained should also be classified as possible.
- 3) **Probable:** the relationship with the use of the device seems relevant and/or the event cannot be reasonably explained by another cause, but additional information can be obtained.
- **4)** Causal relationship: the adverse event can be reasonably associated with the device under study, the comparator or the procedure with the protocol(the relationship cannot be excluded) when:
 - The event is known to be a side effect of the product category to which the device under investigation belongs or to a similar device and/or protocol.
 - The event has a temporal relationship with the use of the medical device under investigation or comparator, or with the procedures involved.
 - The event affects a part of the body or an organ which is expected to be affected by the device or the protocol.
 - The event follows a response pattern known to the medical device (if the response pattern is already known).
 - Stopping the use of the medical device or reducing the level of use (when clinically possible) and then resuming its use or increasing its use had an impact on the event.
 - The event cannot be attributed to any other cause (e.g. an underlying or concomitant disease/health condition, the effect of another device, another drug, another treatment or another risk factor).
 - The damage suffered by the subject is clearly due to an error in use.

• The event depends on a false result given by the device under investigation used for diagnosis (if applicable).

• In order to establish a causal link, it is not necessary for all of the above criteria to be met; it depends on the type of device/protocol and the event.

14.2.4. Type and duration of follow-up of subjects after an AE

AEs will be followed by the Investigator until they are resolved (i.e. the event is resolved or the pathology is unlikely to change or the subject is lost to follow-up). All clinical and biological examinations deemed necessary by the investigator will continue until the patient returns to normal. The investigator will provide the sponsor with copies of all examination results and treatments related to the follow-up of events.

14.2.5. Reporting of serious adverse events (SAEs) to the sponsor:

As part of this category 1 research involving human beings, the investigator is obliged to notify the sponsor immediately, and for no more than 3 calendar days, of any serious adverse event occurring during the study in an included patient (MDCG 2020-10/1). The people who should be contacted are listed in the 14.5 section.

1/ Initial declaration:

This initial report should be made on a paper form entitled "Initial report of a serious adverse event" (blank form kept in the Trial Master File of the investigating site), indicating the date of occurrence, the severity, the relationship with the device under investigation or comparator (or the protocol) and the follow-up. The narrative report must be completed and sent to the CRO and the sponsor as soon as any new relevant information is obtained. Depending on the nature and seriousness of the event, anonymized copies of the patient's source documents may be attached. The information to be collected on the paper form for the initial notification of an SAE is as follows:

- Clear identification of the Investigator/Rapporteur with all contact details,
- Detailed identification of the subject (patient identifier in the study, site number, patient age at the start of the SAE, sex),
- Subject treatment group (device under investigation or comparator),
- Date of endodontic treatment (start date of treatment and date of root canal filling if different from start date),
- Description of the event (free text): nature of the symptoms observed, duration and severity of
 the symptoms, date of onset of the first signs of the AE (before it becomes an SAE), patient
 history and current treatments,
- The reason why this event is considered serious,
- The Investigator's opinion on the imputability of the medical device under investigation or the comparator or the investigation protocol (unrelated, possible, probable, certain),
- Corrective action and treatment.

The status of the SAE must be classified as follows:

- Resolved,
- Resolved with sequelae,
- In progress,
- Death.

The date on which the AE was resolved must be added; if the AE is still in progress, "Not Applicable" should be entered.

Following submission of the initial paper report form, the Investigator/Rapporteur must respond to any follow-up requests or queries from the Sponsor in relation to the SAE within the same timeframe as for the initial report. All the above contacts will be systematically copied on any exchanges concerning an SAE.

The Investigator must also report all SAEs in the eCRF by completing an AE form page.

If the SAE results in the patient being withdrawn early from the study, the Investigator must give details of the reason in the comments section of the initial paper declaration form.

2/ Follow-up declaration:

The Investigator must draw up a specific clinical report and complete and send the "follow-up SAE form" to the CRO and the sponsor within the same timeframe as mentioned above. Test results and hospital reports should be sent to the e-mail addresses listed in the 14.5 section. SAEs must be monitored until they are resolved or stabilized.

3/ After completion of the study:

All SAEs, whatever their relationship with the medical device or the protocol, occurring within 30 days of the last visit of each patient must be notified to the Sponsor in the same way as mentioned above. Any event occurring at any time after the end of the study for a subject who participated in the study and which could be related to the medical device under investigation in the opinion of the Investigator should also be reported to the CRO and the Sponsor.

14.2.6. Urgent safety problem

Any serious threat to public health (as defined in section 14.1) must be reported immediately to the sponsor (contact persons: See section 14.5).

14.2.7. Pregnancy

Pregnancies occurring after the date of signature of the informed consent and up to study discharge (whether early or not) will not be considered a serious adverse event insofar as no genotoxic effect of the medical device under investigation or comparator has been demonstrated; they will be recorded by convention in the AE pages of the eCRF.

14.2.8. Responsibility of the sponsor:

The sponsor will also comment on the relationship between each adverse event and the device under investigation or comparator or the investigation procedures as defined in paragraph 14.2.3. The sponsor will comment on the significance of the serious adverse events it reports and the consequences it draws from them, particularly with regard to the conduct of the research.

The sponsor will maintain detailed records of all adverse events reported by investigators and transmitted by the CRO.

In accordance with Article 80 of Regulation (EU) 2017/745 on medical devices, the sponsor will promptly notify all Member States in which the clinical investigation is ongoing (France and Belgium) of all SAEs and defects that could have led to an SAE in the absence of appropriate action or intervention, or if circumstances had been less favorable.

The sponsor will pass on to the study investigators any information likely to affect the safety of individuals. Serious adverse events must be monitored and documented until the disease has stabilized or returned to normal.

The Sponsor will send periodic safety reports to the Competent Authority and the Ethics Committee in accordance with the company's standard operating procedures with respect to EU regulations taking into account specific local requirements or regulations of the territory where the study is conducted. The Sponsor will respond to all requests from the Competent Authority or the Ethics Committee. The reference document for the medical device under investigation will be the latest instructions for use in force. These reference documents will need to be adapted during the course of the study, if necessary.

14.3. Process for reporting device faults.

All defects in the medical device under investigation or comparator must be recorded in the CRF by the investigator (forms provided for this purpose); defects which did not lead to an adverse effect but which could have caused a clinical event must also be recorded.

The investigator/rapporteur should describe the problems of the device as precisely as possible, avoiding ambiguities and abbreviations. On the basis of this information, the CRO will code each defect according to Appendix A of the IMDRF dictionary with a level 2 or 3 accuracy (IMDRF, 2020).

The sponsor will keep detailed records of defects which are reported by investigators and transmitted by the CRO.

Procedure to be followed by the investigator in the event of failure of the device under investigation (PA1704):

In the event of a defect such as (non-exhaustive list):	The investigator must:					
Difficulty extruding PA1704 from the syringe	Attempt to extrude PA1704 onto a plate; if this does not work, remove the tip of the syringe and attempt to extrude onto the plate again.					
	Then, before use, the investigator visually assesses the texture of the PA1704 cement on the plate.					
	If the texture is satisfactory, apply the cement in the root canal using a new endodontic tip.					
	If the texture of the PA1704 is not satisfactory, do not use the device; put the faulty syringe in the syringe collection box and take another new syringe. Note the reason for the discrepancy on the defect form.					
Low viscosity, the product flows by itself.						
Product out of phase in the syringe (visual assessment of the texture of PA1704 by the investigator).	Do not use the device; put the faulty syringe in the syringe					
Impossible to extrude PA1704 cement, even after trying on a plate (see ^{1st} line).	collection box and take another new syringe.					
Damaged syringe (broken, cracked) after visual inspection when the box is opened.						

Table 8: Action to be taken by the investigator in the event of device failure under investigation (PA1704)

14.4. List of foreseeable adverse events and anticipated adverse device effects, their probable incidence, means of mitigation or treatment.

List of possible AEs (linked to DMs):

Not known

List of foreseeable adverse events (linked to surgical procedures):

Anesthetic protocol: reactions linked to high plasma uptake of the anesthetic, for example in the
event of inflammation at the injection site or accidental intravascular administration (tremors,
dizziness, malaise), local reactions at the injection site.

- Mechanical treatment of the canal: fracture of an instrument in the canal, ingestion of an instrument.
- Allergy, irritation following ingestion of disinfectant solution in the canal (usually hypochlorite).
- 14.5. Emergency contact details for reporting serious adverse events and serious adverse device effects.

The investiga	tor must notify SLB PHARMA	by telep	ohoi	ne on			or by e-i	mail to the vig	ilance
department	ру	e-mail	to	the	sponsor's	drug	safety	department	

14.6. Information on the Data Monitoring Committee, if established.

Not applicable.

15. Vulnerable population

✓ Description of the vulnerable population concerned by the study

Not applicable

✓ Description of the specific process for obtaining informed consent.

Not applicable

✓ Description of the specific responsibility of the ethics committee.

Not applicable

✓ Description of any medical care provided to subjects once the clinical trial has been completed.

Patients continue to be treated by their regular dental surgeon.

16. Premature termination or suspension of clinical trial

✓ Criteria and provisions concerning premature termination or suspension of the clinical trial for the investigation as a whole or for one or more sites.

The reasons for temporary or permanent early termination of the trial are as follows:

- decision of the Sponsor,
- decision by the person directing and supervising the trial (the coordinator),
- decision of the institution responsible for the trial.

✓ Criteria for accessing and breaking the blinding code due to suspension or premature termination of the clinical trial, if this involves a blinding technique.

Not applicable (no blinding of products).

✓ Subject monitoring requirements.

Patients will be monitored in accordance with standard practice.

17. Publication policy

✓ Statement as to whether the results of the clinical trial will be published.

The results may be published.

✓ Statement indicating the conditions under which the results of the clinical trial will be published.

Communications and scientific reports relating to this clinical study will be produced under the responsibility of the sponsor, with the agreement of the investigators. They will draw up a list of authors. Publication rules will follow international recommendations (N Engl J Med, 1997).

Any publication of the results will be strictly anonymous with regard to the participating subjects.

At the end of the clinical study, subjects may be informed of the overall results of the research on simple request to the investigator in charge of their follow-up.

18. Bibliography

AAE Guideline 1994 ()

National Agency for the Development of Medical Evaluation. Dental recommendations and references. Paris: ANDEM, 1996. (URL: www.anaes.fr)

APPENDIX 1: INSTRUCTIONS FOR USE PA1704

APPENDIX 2: CE BIOROOT™ RCS CERTIFICATE

APPENDIX 3: NOTICE D'UTILISATION BIOROOT™ RCS

APPENDIX 4: DECLARATION DE CONFORMITE AU REFERENTIEL MR-001

APPENDIX 5: ASSURANCES (FRANCE + BELGIQUE)

Appendix 1: Instructions for use PA1704

Instructions for using PA1704 filling cement and precautions.

Injection of PA1704 into the root canal:

- 1/ Clean the root canal and shape it using standard endodontic procedures.
- 2/ Select a master gutta-percha cone and check that it fits the length of the working area
- 3/ Rinse with sterile saline solution to remove any residual irrigation solution, then dry without completely dehydrating the root canal.
- 4/ Open the protective sachet and take out the syringe.

Note the patient identifier on the label (PATIENT $_$ $_$ $_$ $_$).

5/ Take out the endodontic tip supplied with the PA1704

CAUTION: It is recommended to use conventional means (techniques) to hold the filling material in the canal with the endodontic tip.

6/ Remove the syringe cap and screw on an endodontic tip as far as it will go.

CAUTION: Make sure that the tip is correctly screwed on to prevent it coming off the syringe during treatment.

7/ The gripping wing can be placed on the syringe to make it easier to push the plunger.

CAUTION: Make sure that the gripping wing is correctly clipped in to prevent it coming off when the material is injected.

[figure not shown]
- 8/ Before injecting the cement into the canal, check that the cement is coming out of the syringe by ejecting a small quantity of material; if the syringe is blocked, do not use it, dispose of it in the syringe recovery box, and complete the defect form in the eCRF.
- 9/ Insert the tip into the canal, up to a maximum of the first third of its length; check that the tip is not stuck in the canal, nor being forced in, then gently inject the material, without forcing it and gradually and slowly withdraw the tip from the canal while continuing to inject the product.
- 10/ Complete the obturation by inserting the master gutta-percha cone (single cone technique) or several gutta-percha cones (lateral condensation technique) to the length required.
- 11/ Assess the quality of the root canal filling by taking a radiograph (intraoperative check),
- 12/ Use a heat source to cut the cone at the entrance to the filled canal.
- 13/ Complete the procedure by lightly condensing the upper part of the gutta cone with a large-diameter vertical endodontic compactor
- 14/ Assess the quality of the root canal filling by taking an X-ray (postoperative check) at T0. The images obtained are to be transferred into the eCRF.

After filling with the PA1704 product:

15/ Perform a sealed coronal restoration.

16/ If it is necessary to fit an anchor pin, this should be done after the PA1704 material has fully hardened in the canal, i.e. 7 days.

Clinical Trial: OPTIFILL Sponsor: Septodont Appendix 5: Assurances (France + Belgique) – contrats initiaux, hors LDA

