2.6. Target population and indications for use

Target population: permanent and mature monoradiculated or pluriradiculated teeth.

Clinical indications:

- Permanent root canal filling in the case of inflamed or necrotic pulp.
- Permanent root canal filling after a re-treatment procedure.

Contraindications:

- Immature or temporary teeth.
- Known hypersensitivity to one of the ingredients.

2.7. Summary of the training and experience required to use PA1704 filling material.

PA1704 is a professional dental product. It should be used by dentists carrying out endodontic treatment, whether they are general practitioners or exclusive endodontists, following the instructions for use given in the following chapter.

2.8. Instructions for using PA1704 filling cement and precautions.

Injection of PA1704 into the root canal:

1/ Clean the root canal and shape it using standard endodontic procedures.

2/ Select a master gutta-percha cone and check that it fits the length of the working area

3/ Rinse with sterile saline solution to remove any residual irrigation solution, then dry without completely dehydrating the root canal.

4/ Open the protective sachet and take out the syringe.

Note the patient identifier on the label (PATIENT _ _ _ _ _).

5/ Take out the endodontic tip supplied with the PA1704

CAUTION: It is recommended to use conventional means (techniques) to hold the filling material in the canal with the endodontic tip.

6/ Remove the syringe cap and screw on an endodontic tip as far as it will go.

CAUTION: Make sure that the tip is correctly screwed on to prevent it coming off the syringe during treatment.

7/ The gripping wing can be placed on the syringe to make it easier to push the plunger.

CAUTION: Make sure that the gripping wing is correctly clipped in to prevent it coming off when the material is injected.

8/ Before injecting cement into the canal, check that the cement comes out of the syringe by ejecting a small quantity of material; if the syringe is blocked, do not use it, dispose of it in the syringe recovery box, complete the eCRF defect form and enter the information in the patient's medical record.

9/ Insert the tip into the canal, up to a maximum of the first third of its length; check that the tip is not stuck in the canal, nor being forced in, then gently inject the material, without forcing it and gradually and slowly withdraw the tip from the canal while continuing to inject the product.

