6.5. Trial procedure

6.5.1. Description of any procedure related to the clinical trial to which people are subjected during the trial.

All examinations, the frequency of dental consultations and the products used, with the exception of the medical device under investigation, are to be standard practice and comply with the latest HAS recommendations (HAS 2008).

This chapter is divided into successive sections:

- Instructions for use of PA1704 and BioRoot™ RCS filling materials (reminder of Chapters 2.8 and 6.2).
- A description of the materials and techniques recommended to achieve a coronal restoration of a temporary and then permanent nature,
- The procedure for patient visits.

✓ Instructions for use of PA1704 and BioRoot™ RCS filling materials

Steps	PA1704	BioRoot™ RCS					
	(Reminder of chapter 2.8)	(Reminder of chapter 6.2 and instructions for use)					
Mixing instructions	Not applicable (ready-to-use cement in syringe)	1. Retrieve some powder using the spoon supplied with the kit. Place a level spoonful of powder on the mixing block.					
		 Release a single dose of mixing solution. Open it by turning the sealed cap. Pour 5 drops of the single dose onto the mixing block. Prepare the root canal cement by gradually adding the powder to the liquid. Mix until a smooth paste is obtained (about 60 seconds). The mixture must be prepared extemporaneously. 					
		4. Rinse and clean used instruments immediately to remove any residual material.					
Injecting the	1. Clean the root canal and shape it using standard endodontic	1. Clean the root canal and shape it using standard endodontic procedures.					
cement into the root canal:	2. Select a master gutta-percha cone and check that it fits the	2. Select a master gutta-percha cone and check that it fits the length of the working area.3. Rinse with sterile saline solution to remove any residual irrigation					
the root canal.							
	3. Rinse with sterile saline solution to remove any residual	solution, then dry without completely dehydrating the root canal.					

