Maximum pain in the first 7 days and time to onset of maximum pain: Description and comparison, between the PA1704 arm and the BioRoot™ RCS arm, of the maximum pain experienced during the 7 post-operative days and its time to onset by a Student, Welch or Wilcoxon test.

Intra-operative pain relief between T0 and D7: Description of painkiller classes, reasons for use, frequency of use and cumulative dose per patient over 7 days. Description and comparison, between the PA1704 arm and the BioRoot™ RCS arm, of the proportion of patients who used *oral* pain medication between T0 and D7 by Pearson's Chi-2 test or Fisher's exact test.

Description of the surgical technique: Description and comparison, between the PA1704 arm and the BioRoot™ RCS arm, of the type of anesthesia, the technique used to remove the old filling material (if root canal re-treatment only), the technique used to shape the canal, the type of disinfectant and rinse solutions used and irrigation techniques, the method of application of filling material and gutta-percha condensation, and the coronal restoration technique, by Pearson's Chi-squared test or Fisher's exact test. Intraoperative complications will be described where appropriate.

Operator comfort and satisfaction: Description and comparison, between the PA1704 arm and the BioRoot™ RCS arm, of operator comfort criteria. Satisfaction will be described at T0 and 2 years, and the proportions of satisfied operators will be compared.

For the performance criteria (efficacy rate, filling density, and material resorption) evaluated at 3.5 years and 5 years in the PA1704 arm: These criteria will only be described.

7.7.6. Safety/tolerance analysis:

The tolerance analysis will focus on the Tolerance population. Tolerance data is to be expressed as the number of adverse events (AEs) and the number of patients reporting at least one AE. Severity, cause (filling material or surgical technique) and the time of occurrence shall be described. The proportions of AEs and patients with AEs will be compared between the 2 groups. The proportions of patients who used an additional dental consultation for significant post-operative complication or pain will be described and compared, between the PA1704 arm and the BioRoot™ RCS arm, by Pearson's Chi-squared test or Fisher's exact test.

Defects in the devices will be described in the form of a list and proportions will be compared between the 2 groups.

7.7.7. Intermediate analyses:

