14.1. Definitions

The definitions below are in line with EN ISO 14155:2011 and Regulation (EU) 2017/745 on medical devices (including guide MDCG 2020-10/1) and current national regulations:

Device failure

Any defect in the identity, quality, durability, reliability, safety or performance of a device under investigation, including any malfunction, any error in use, or any defect in the information provided by the manufacturer.

Adverse event (AE)

Any adverse clinical event, unintended illness or injury, or any untoward clinical sign (including an abnormal laboratory finding) in participants, users or others, in the course of a clinical investigation, whether or not related to the device under clinical investigation.

- NOTE 1: This definition includes events related to the medical device under investigation or to the comparator.
- NOTE 2: This definition includes events linked to the procedures involved.
- NOTE 3: For users or other persons, the definition concerns only events linked to devices under investigation and comparator.

Adverse device effect (ADE)

Adverse event linked to the use of medical devices under investigation and comparator.

NOTE 1: This definition includes any adverse event resulting from insufficiencies or inadequacies in the instructions for use, deployment, implantation, installation and operation, or any malfunction of the medical device.

NOTE 2: This definition includes any event resulting from an error of use or intentional improper use of the medical device.

Serious adverse event (SAE)

Any adverse event leading to:

- a) death;
- b) a serious deterioration in the participant's state of health:
 - i) a life-threatening illness or injury;
 - ii) a permanent impairment of an anatomical structure or function;
 - iii) hospitalization or prolongation of the patient's hospitalization;
 - iv) medical or surgical intervention to prevent any life-threatening illness or injury or any permanent impairment of an anatomical structure or function;
 - v) a chronic illness;
- c) fetal distress, fetal death, congenital physical or mental impairment or congenital malformation;

NOTE: A planned hospitalization due to a pre-existing condition or a procedure required by the clinical investigation plan, without any serious deterioration in health, is not considered to be an SAE.

Serious adverse device effect (SADE)

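### The structured prompts to detect and report device defects are written only for PA1704, so the planned between-arm comparison of defect proportions is open to detection bias against it

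*Combined protocol and SAP*

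**What the plan says.** **PA1704.** Step 8 of the instructions (section 2.8, Table 5 in 6.5.1, Appendix 1) has the investigator "check that the cement is coming out of the syringe by ejecting a small quantity of material" before injection. The consequence of a failed check follows directly: "if the syringe is blocked, do not use it, dispose of it in the syringe recovery box, and complete the defect form". Section 14.3 adds Table 8, titled "Action to be taken by the investigator in the event of device failure under investigation (PA1704"), which lists difficult or impossible extrusion, low viscosity, phase separation and a damaged syringe. Section 11 has used and unused PA1704 syringes counted at site monitoring visits.

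**BioRoot RCS.** The mixing row of Table 5 says "Mix until a smooth paste is obtained (about 60 seconds"). The readable BioRoot column contains no accept-or-discard step and no reference to the defect form.

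**Definition and duty to record.** Section 14.1 defines device failure as "Any defect in the identity, quality, durability, reliability, safety or performance of a device under investigation"; the comparator is not named, although the adverse event and adverse device effect definitions beside it do name it. Section 14.3 is wider: "All defects in the medical device under investigation or comparator must be recorded in the CRF by the investigator (forms provided for this purpose"). It includes defects that caused no adverse effect but could have caused a clinical event.

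**Analysis.** Section 7.7.6 states: "Defects in the devices will be described in the form of a list and proportions will be compared between the 2 groups". The Statistical Methods part of the synopsis says the same. No denominator is given.

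**The concern.** A comparison of defect proportions is fair only if a defect of either device has the same chance of reaching the database. In the PA1704 arm a specific test is made on every syringe, its failure leads to a form, a table says what counts as a defect, and each syringe serves one patient and carries that patient's identifier. In the BioRoot arm an unsatisfactory mix could be repeated from a kit shared by several patients (section 6.2). Whether that is reported depends on the investigator regarding it as a defect, and neither 14.1 nor Table 8 says that it is one.

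At stake is one safety comparison. The number of faults is a listed secondary measure (Table 3), in a trial meant to show that the change of presentation does not affect performance or safety. A significant PA1704 excess arising from closer inspection would be an awkward finding to explain in a pre-marketing file.

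**Working it through.** **Inputs from the protocol.** 80 patients per arm (6.2, 7.2); secondary tests two-sided at 5% (7.3); Pearson chi-square, or Fisher's exact test if any expected count is below 5 (7.7.3). Section 7.7.6 names no test for defects, so the general rule is applied.

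**The plan's own figure.** No defect rate or power is stated for this comparison; the only figure to reproduce is the sample size. For non-inferiority with 90% in both arms, margin 0.13, one-sided 5% and 80% power: n = (1.645 + 0.842)² × 2 × 0.9 × 0.1 / 0.13² = 6.18 × 0.18 / 0.0169 ≈ 65.9, so 66 per group. Adding 20% gives 66 × 1.2 = 79.2, so 80. It reproduces.

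**Assumptions.** The unit is the patient with at least one recorded defect. The true rate p is the same in both arms. All PA1704 defects are recorded; a fraction c of BioRoot defects is recorded. Neither p nor c is in the documents, so both are varied.

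**Model.** X (PA1704) ~ Binomial(80, p) and Y (BioRoot) ~ Binomial(80, c·p), independent. The quantity wanted is the sum of P(X = x)·P(Y = y) over all pairs with x > y and test p-value below 0.05, by exact enumeration.

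**What significance requires.** The smallest significant PA1704 excesses are 6 v 0 (p = 0.028; 5 v 0 gives 0.059), 8 v 1 (0.034), 9 v 2 (0.029) and 10 v 3 (0.043). At p = 2% the expected PA1704 count is 80 × 0.02 = 1.6, far short of six. At p = 10% it is 8, against an expected 80 × 0.10 × 0.25 = 2 for BioRoot when a quarter are captured; 8 v 2 gives p = 0.050, on the boundary.

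**Chance of a significant PA1704 excess when the true rates are equal:**

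| True rate p | c = 1 | c = 0.5 | c = 0.25 |
|---|---|---|---|
| 2% | 0.1% | 0.3% | 0.4% |
| 5% | 1.1% | 4.7% | 9.8% |
| 10% | 2.4% | 19.6% | 43.2% |
| 20% | 2.5% | 42.3% | 84.9% |

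With milder loss (c = 0.8) the chance is 1.9% at p = 5% and 6.0% at p = 10%. With no BioRoot defect recorded at all (c = 0), it is still only 0.5% at p = 2%.

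**The case against.** The strongest reply is that comparator defects are already covered. Section 14.3 makes recording mandatory for both devices and provides forms; the opening of section 14 requires all device defects to be reported; the vigilance row of Table 7 has no arm restriction; and under 6.6.5 the CRAs verify defects and have access to both products. BioRoot boxes are also collected and counted, though only at the end (section 11). Operators in both arms are asked at T0 about handling and difficulties encountered (Table 3). All of this stands. It rules out the reading that BioRoot defects are recorded only spontaneously: no section says so.

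Other parts of the reply also stand. A blocked syringe would probably show itself on injection, so step 8 mainly moves the moment of detection; Table 8 is the stronger source of asymmetry. Mixing to a smooth paste is itself a consistency criterion. The numbering of the BioRoot steps in Table 5 goes from 6 to 8 in the readable text, and the BioRoot instructions in Appendix 3 are not reproduced, so the absence of a BioRoot check is established only for what can be read. Fuller defect instructions are to be expected for a device used in patients for the first time.

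What survives is narrower. A duty to record does not equalise detection when one device has named triggers and the other has none, and 14.1 and 14.3 differ on whether the comparator is in scope.

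A reader might also infer that a real advantage of the ready-to-use form would be hidden. In an extreme case it could be: with true rates of 5% for PA1704 and 20% for BioRoot, capturing a quarter of BioRoot defects gives a recorded rate of 0.20 × 0.25 = 5%, equal to PA1704, and power in the correct direction falls from 85% to 1.1%. The documents do not support those rates or that capture, and the operator questions give a second route for such trouble to be seen.

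**Conclusion.** The point holds as a risk of detection bias in one secondary safety comparison. A reader might infer that two equally reliable devices will show a significant PA1704 excess; the documents do not support that, because recording is mandatory in both arms and the loss of BioRoot defects is assumed, not shown. The size depends on two unknowns. At a true rate of 2% the problem is negligible whatever the capture. At 5% the chance of a false excess is about 5% to 10% if a quarter to a half of BioRoot defects are captured. It becomes serious at about 10% and above with that degree of loss (20% to 43% at 10%, 42% to 85% at 20%), against at most about 2.5% in that direction with equal capture. These figures assume equal true rates, full PA1704 capture and counting by patient.

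The non-inferiority conclusion rests on the 2-year efficacy rate and is not touched. The change is worth making because it is cheap, not because the trial depends on it.

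**What to change.** 1. Align the device-failure definition in 14.1 with 14.3 so that it covers the comparator. Put the same short defect checklist on the eCRF for every patient in both arms, including whether a device or mix was discarded or replaced before use (yes/no, with the reason). This changes recording only; how either device is used stays as it is.
2. If patients have already been treated without the checklist, describe defects by device and type, and delete the between-arm comparison of defect proportions from 7.7.6 and the synopsis.

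The cost is a few tick-boxes per patient under the first option, or the loss of one secondary test under the second. Sample size and the primary analysis do not change.
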